9.2 Laboratory Evaluations/Assays

9.2.1 Immunogenicity Evaluations

Serum hemagglutination-inhibition (HAI). HAI will be performed in microtiter format using turkey RBCs and egg-grown, betapropiolactone-inactivated A/California/07/09 virus as antigen. The titer of antibody will be defined as the highest dilution resulting in complete inhibition of hemagglutination. Sera will be treated with receptor-destroying enzyme and heat inactivated prior to testing at an initial starting dilution of 1:4. Sera with no detectable HAI titer will be assigned a titer of 1:2 for calculation purposes.

Microneutralization (MN) assay: Sera will be tested by microtiter technique for neutralization of an A/California/07/09 x PR8 reassortant virus in MDCK cells. Viral growth will be determined by ELISA of the cells following fixation with methanol using a combination of M- and NP-specific monoclonal antibodies. The titer of antibody will be defined as the highest titer resulting in 50% inhibition of antigen signal compared to un-neutralized control wells. Sera will be treated with RDE and heat inactivated prior to testing at an initial starting dilution of 1:10. Sera with no neutralizing titer will be assigned a value of 1:5 for calculation purposes.

B cell responses: Peripheral Blood Mononuclear Cells (PBMC) will be obtained before and on day 7 and 28 after vaccine and evaluated for B-cell responses. B cell responses will be evaluated by memory cell assay [16] and antibody secreting cell assay. In addition, B cells will be cultured in vitro and the functional quality of secreted antibody assessed by HAI and MN assays

CD4 T cell responses: PBMCs collected prior to and on day 3, 7, 14 and 180 after vaccination will be evaluated for the presence of antigen specific CD4 cells by ELISPOT assay and flow cytometry using a panel of peptides spanning the H1 hemagglutinin, neuraminidase and internal virion proteins such as NP and M1 [17]. This assay will identify both cross reactive and H1 specific epitope responses, as well as recall of memory cells to conserved internal virion proteins. PBMC will also be evaluated for the presence of antigen specific ELISPOT and cell homing markers by flow cytometry.

9.2.2 Specimen Collection, Preparation, Handling and Shipping

Instructions for specimen preparation, handling, and storage are included in the Manual of Procedures (MOP). Instructions for specimen shipment are included in the MOP.

9.3 Procedures to be Followed in the Event of Abnormal Laboratory Test Values or Abnormal Clinical Findings

Urine or serum pregnancy tests will be performed within 24 hours prior to vaccination on all female subjects of childbearing potential (see above). Subjects with positive pregnancy tests are not eligible to participate. No other screening or clinical laboratory tests will be routinely obtained.

10 ASSESSMENT OF SAFETY

10.1 Specification of Safety Parameters

Only FDA approved, licensed seasonal inactivated influenza vaccine will be administered in this protocol as standard of care during influenza vaccine season, following the manufacturers' instructions and safety precautions. No serious adverse events are anticipated to occur to study participants as a result of this protocol.

Adverse events (AEs) related to administration of influenza vaccine include (as per Package Insert) injection site reactions (pain, swelling and erythema) and systemic reactions (headache body ache and muscle weakness). Since immunization with influenza vaccine is offered as standard of care to healthy adults, these anticipated reactions to the vaccine will not be considered reportable adverse events. Events meeting VAERS reporting requirements will be reported as indicated below.

There are minimal risks associated with venipuncture for obtaining research related labs. Foreseeable adverse events associated with venipuncture are: mild, temporary discomfort at the venipuncture site, bruising, and phlebitis. Very rarely, patients may experience vaso-vagal syndrome during phlebotomy. Vaso-vagal reactions may include diaphoresis, nausea, syncope and rarely loss of consciousness. These events will not be collected. However, severe vaso-vagal reaction, including loss of consciousness or > grade 2 hypotension will be reported as adverse events of special interest.

Any other adverse events that meet the reporting requirements of the Institutional Review Board will also be reported to DMID Medical Officer and the Clinical Project Manager.

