4 OBJECTIVES AND OUTCOME MEASURES

4.1 Study Objectives

Primary Objective

- Comparison of the serum antibody response to immunization with pure HA, cell-derived and egg derived subvirion vaccines in adults age 18-49 years
- Comparison of the HA- specific CD4 T cell response in adults receiving pure HA, cell-derived vaccine egg-derived split or subvirion vaccines

Secondary Objectives

- Comparison of the epitope specificity of B cells following vaccination with HA or subvirion vaccines

Evaluation of the different vaccine formulations to induce HA specific antibodies that recognize circulating viruses

Exploratory Objective

- Confirmation of the safety of the licensed vaccines in healthy adults
-
- Evaluation of the effect of repeated vaccination on the immune response

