4.2.2 Secondary Outcome Measures

Secondary and tertiary outcome measures are listed below:

Secondary Outcome Measures

[figure not shown]
- Antibody specificity of cloned plasmablasts from subjects in each group
-
- Correlations of CD4 T cell ELISPOT number (Day 0 to Day 14) and antibody titers (Day 0 to Day 28) in subjects from each group (year 1-3), R value per cohort will be reported

Tertiary Outcome Measure

- Vaccine related adverse events
- Mean change in the CD4 T cell reactivity to pools of total pHA peptides derived from the pH1N1 HA, as well as H3, influenza B HA, NP, and M1 peptides will be quantified using cytokine Elispot from Day 0 to Day 14 for subjects with successive years of vaccination

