7 STUDY INTERVENTION/INVESTIGATIONAL PRODUCT

7.1 Study Product Description

Fluzone Standard Dose (Sanofi Pasteur). Quadrivalent subvirion vaccine (IIV4) produced in embryonated hen's eggs and administered intramuscularly at a dose of 15 ug of HA (as determined by SRID) per component.

Fluzone High Dose (Sanofi Pasteur). Trivalent subvirion vaccine (IIV3) produced in embryonated hen's eggs and administered intramuscularly at a dose of 60 ug of HA (as determined by SRID) per component.

FluCeIVax (Novartis). Quadrivalent subunit vaccine produced in MDCK mammalian cell culture (ccIV4) administered intramuscularly at a dose of 15 ug of HA (determined by SRID) per component

FluBlok (Protein Sciences) Quadrivalent purified recombinant hemagglutinin vaccine (rIV4) produced in insect cells and administered intramuscularly at a dose of 45 ug of HA (determined by SRID) per component.

All four products are indicated for the prevention of influenza in adults, although Fluzone HD is only indicated for prevention in adults ages 65 and older.

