8.3.3 Day 14 visit (\pm 1 day)

Subjects will return for follow up approximately 14 days after vaccination for assessment of the immune response. At that visit, the following procedures will be performed.

- Interval medical history will be obtained including concomitant medications, reviewing any new events since the last visit. If indicated by history, a relevant physical exam will also be performed.
- Any adverse events (AE) will be recorded as described in the safety section 10.1 and appropriate corrective actions taken if indicated
- Peripheral Blood Mononuclear Cells (PBMC) will be collected from an arm vein for assessment of the CD4 T cell response to vaccination

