16.3 Types of Data

Data for this study will include subject demographics, safety assessments including reactogenicity events after vaccination, and research laboratory results including antibody responses and measurements of B cell, CD4 cell, and transcriptional responses.

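### The plan contradicts itself on whether expected vaccine reactions are recorded and counted in the tertiary outcome of vaccine-related adverse events

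*Combined protocol and SAP*

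**What the plan says.** Section 4.1 includes "Confirmation of the safety of the licensed vaccines in healthy adults" as an exploratory objective; the protocol summary calls it tertiary. The matching tertiary outcome in 4.2.2 is "Vaccine related adverse events", with no definition, time window or grading.

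Section 10.1 first identifies the adverse events related to influenza vaccine: local pain, swelling and erythema, plus headache, body ache and muscle weakness. It then states that "these anticipated reactions to the vaccine will not be considered reportable adverse events". The ground given is that immunization is offered to healthy adults as standard of care. The section opens on the same note: "Only FDA approved, licensed seasonal inactivated influenza vaccine will be administered in this protocol as standard of care", following the manufacturers' instructions.

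Sections 8.3.1 to 8.3.4 (Days 3, 7, 14 and 28) all use the formula "Any adverse events (AE) will be recorded as described in the safety section 10.1". Early termination (8.4) and unscheduled visits (8.5) also refer to 10.1.

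Other places are broader. Section 16.3 lists "safety assessments including reactogenicity events after vaccination" as study data. Section 10.4 calls for monthly line lists of all adverse events, and 10.5 puts non-serious events in the annual report. The Day 180 visit (8.3.6) records adverse events without reference to 10.1.

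On the high-dose vaccine, section 7.1 says that "Fluzone HD is only indicated for prevention in adults ages 65 and older". Section 6.1 sets the age for new subjects at 18 to 49.

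**The concern.** The reactions that 10.1 names as vaccine-related adverse events are the same ones it then sets aside as not reportable. Because the visits take their recording rule from 10.1, a coordinator who follows 8.3 and 10.1 could record no injection-site pain or headache, while one who follows 16.3 would record both. The study runs for several seasons, so capture could differ between staff or between years, and the event counts would then be hard to interpret.

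The high-dose arm makes this more than a matter of wording. Section 3.4.1 expects slightly more mild local reactions with high-dose vaccine, and those belong to the class made non-reportable. The justification in 10.1 is also weakest for this arm, since the product is given to new subjects below its indicated age. If the narrow reading were followed, a short event table could be taken as confirmation of safety although the common reactions had been left out by rule.

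**Working it through.** The documents give no reaction rate, safety sample size or safety power, so there is no figure to reproduce. The main check is of wording.

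**Step 1. Passages side by side**

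| Points to expected reactions being left out | Points to their being recorded |
|---|---|
| 10.1: expected reactions are not reportable | 16.3: reactogenicity is study data |
| 8.3.1 to 8.3.4, 8.4, 8.5: recording follows 10.1 | 8.3.6: Day 180 recording does not refer to 10.1 |
| 9.1: targeted examination is for assessing events that need VAERS reporting under 10.1 | 10.4: monthly line lists of all adverse events |
| 10.2: the only safety form named is the VAERS/AESI case report form | 10.5: non-serious events go in the annual report |
| 12.4: no analysis of adverse events | 8.3.1 to 8.3.4: interval history covers new events |

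Neither column overrides the other. No passage says whether expected reactions count in the tertiary outcome, and none describes a symptom list, grade or window for them.

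**Step 2. What is captured on either reading.** VAERS-reportable events, severe vaso-vagal reactions and the other listed events of special interest, reactions the investigator judges unexpected, and events reportable to the IRB (10.1, 10.2). Serious events are notified immediately (10.4).

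**Step 3. What those remaining events could show.** Assume 45 recipients, the group size in the CD4 power statement of 12.2, which is not a safety sample size.

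- Chance of at least one event, 1 - (1 - p)^n: for an assumed p of 1 per 1,000, 1 - 0.999^45 = 4.4%; for 1 per 100, 1 - 0.99^45 = 36%.
- With no events, the one-sided 95% upper bound is 1 - 0.05^(1/45) = 6.4%.

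Few such events per arm are therefore plausible, but the event rates are assumptions. An empty list of these events would say nothing about common reactions.

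**Step 4. What recording expected reactions would give.** The half-width of a 95% interval is 1.96 × sqrt(p(1 - p)/n), with n = 45 and assumed rates:

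- p = 10%: 1.96 × sqrt(0.10 × 0.90/45) = 0.088
- p = 30%: 1.96 × sqrt(0.30 × 0.70/45) = 0.134
- p = 50%: 1.96 × sqrt(0.50 × 0.50/45) = 0.146

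That is about 9 to 15 percentage points. Enrolment may reach 500 (section 6), so arms could be larger. An equal split over four vaccines, used only for illustration, gives 500/4 = 125 per arm and half-widths of 0.053 (p = 10%) to 0.088 (p = 50%).

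**Step 5. The procedures table.** Section 8.3.3 requires an interval history and adverse event recording at Day 14. The Section 19 table marks neither there, although it marks the directed examination. This is a separate, minor inconsistency.

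**The case against.** The strongest reply is that not reportable does not mean not recorded. Section 10.1 states outright that routine venipuncture events are not collected, and it does not use that language for vaccine reactions. Together with 8.3.6, 10.4, 10.5 and 16.3, this supports the view that expected reactions are recorded and merely exempt from onward reporting. The full content of the case report forms is not in the documents, so the lack of a field for these reactions is not shown either. This stands.

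It rules out three stronger conclusions that a reader might draw: that the safety objective cannot be answered, that no reaction rate is estimable, and that the outcome table will be close to empty. The first two hold only if the narrow reading is followed, and even then serious, special-interest and unexpected events are captured. The third would need event rates that the documents do not give.

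A second reply is that the outcome is tertiary and that section 5 disclaims any formal comparison of adverse event profiles. That limits the weight of the point but withdraws neither the objective nor the outcome, and a descriptive table is not a formal comparison.

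Third, section 3.4.1 openly says that high-dose vaccine is not indicated under 65 and cites experience in healthy adults. This stands too. What remains is that the rationale in 10.1 does not agree with 3.4.1 and 7.1.

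Finally, the text could equally be reconciled by narrowing the outcome to reportable events. That would be consistent, but it would leave out the reactions that the protocol itself expects to be more frequent with high dose.

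**Conclusion.** The contradiction is real and worth correcting, at low severity. Sections 8.3 and 10.1 support a reading in which expected reactions fall outside the tertiary safety outcome. Section 16.3, with support from 8.3.6, 10.4 and 10.5, supports the opposite. As written, the plan does not settle which applies, on which form, over what window, or whether these reactions count in the outcome. The documents do not show that the reactions will go unrecorded, only that staff could properly follow either reading. The standard-of-care sentence in 10.1 does not fit Fluzone HD as described in 3.4.1 and 7.1.

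The figure of 9 to 15 percentage points rests on three assumptions: 45 subjects per arm, reaction rates of 10% to 50%, and one vaccination counted per subject. It shows that recording would be useful for description. It does not measure a loss that is certain to occur.

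**What to change.** - Keep the exemption of expected reactions from expedited reporting.
- State in 10.1 and 8.3 that expected injection-site and systemic reactions are recorded on the case report form at the existing Day 3, 7 and 14 visits, and that they count in the tertiary outcome. Specify the symptom list, grade and window.
- Add to 12.4 a descriptive table of these reactions by vaccine arm with 95% intervals and no formal comparison. State how re-enrolled subjects are counted.
- Bring 10.4, 10.5, 16.3 and 8.3.6 into line with this wording.
- Reconcile the standard-of-care sentence in 10.1 with 3.4.1 and 7.1.
- As a minor correction, add the Day 14 interval history and adverse event review to the Section 19 table, to match 8.3.3.

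The cost is a short checklist at visits already scheduled, one added table and some wording. No new visit or blood draw is needed.

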10.2 Safety Reporting: VAERS and Adverse Events of Special Interest (AESI)

The investigator must report the following events to VAERS with a copy to the DMID Medical Officer, and the Clinical Project Manager will be notified by email, including a copy of the report (VAERS form). In addition, these events will be reported on the VAERS/AESI case report form:

- Any adverse event listed by the vaccine manufacturer as a contraindication to further doses of the vaccine (Severe allergic reaction: e.g. (Anaphylaxis or anaphylactic shock 7 days post-vaccination) encephalopathy or encephalitis: e.g. coma, decreased level of consciousness, prolonged seizures within 7 days of vaccine administration, Guillain-Barre syndrome within 6 weeks of vaccination, Arthus-type hypersensitivity reaction),

-
- Any adverse event listed in the VAERS Table of Reportable Events Following Vaccination found using the following link: https://vaers.hhs.gov/docs/VAERS_Table_of_Reportable_Events_Following_Vaccination.pdf.
 - Brachial neuritis (28 days)
 - Any acute complications or sequelae (including death) of above events that occurs within the specified time period after vaccination,
 - In the judgment of the PI, any unexpected reaction to the vaccine will be reported to VAERS as well as the DMID Medical Officer and the Clinical Project Manager.

The investigator must also report the following adverse events of special interest (AESI) on the VAERS/AESI case report form, and to DMID CPM and DMID Medical Officer. However, these events do not meet criteria for VAERS reporting:

- Severe vaso-vagal reaction following venipuncture, including loss of consciousness or > grade 2 hypotension.
- Infection or inability to breast feed following the use of the breast pump.

All adverse events that meet the reporting requirements of the Institutional Review Board will also be reported to DMID Medical Officer and the Clinical Project Manager.

10.3 Procedures to be Followed in the Event of Abnormal Laboratory Test Values or Abnormal Clinical Findings

Urine pregnancy tests will be performed within 24 hours prior to vaccination on all female subjects of childbearing potential (see above). No other screening or clinical laboratory tests will be routinely obtained.

10.4 Reporting Procedures

ICH GCP 6, Section 4.11 require that an investigator notify the sponsor, regulatory authority(ies) and the local IRB immediately of any serious adverse event, deaths, or life-threatening problems that occur in the study. Adverse events and/or laboratory abnormalities identified in the protocol as critical to safety evaluations should be reported to the IRB in accordance with reporting requirements specified by the IRB. Line lists of all adverse events and/or laboratory abnormalities will be reported via email to the DMID Clinical Project Manager and Medical Officer on a monthly basis.

10.5 Other Adverse Events (if applicable)

Non serious adverse events will be reported with the annual report for the study

10.6 Reporting of Pregnancy

Pregnancy events will be reported with the annual report of the study. All pregnancies will be followed to termination and the result of the pregnancy will be recorded in the study record.

10.7 Type and Duration of Follow-up of Participants after Adverse Events

All adverse events and serious adverse events will be followed until resolved, return to baseline or stable as determined by the study team.

11 CLINICAL MONITORING

Purpose: to protect the rights and well-being of human subjects in this study; to ensure that data are accurate, complete and verifiable from source documents; to ensure that conduct is in compliance with the currently approved protocol/amendments, with Good Clinical Practice, and with regulatory requirements.

11.1 Site Monitoring Plan

Site monitoring will be conducted using the DMID tools provided to ensure that human subject protection, study procedures, laboratory procedures, and data collection processes are of high quality and meet sponsor, GCP/ICH, and regulatory guidelines, and that the study is conducted in accordance with the protocol and sponsor standard operating procedures. DMID, the sponsoring agency, or its designee will conduct site-monitoring visits as defined in the CQMP.

A protocol-specific Clinical Quality Management Plan (CQMP) has been approved for this study by DMID. The Quality Assurance (QA) plan will be implemented by a weekly review of source documents by the CRC to determine adherence to protocol requirements. The Quality Control (QC) plan will be implemented by daily observation and documentation of the site's work processes by study staff, to ensure that accepted procedures are followed.

Site visits may be made at standard intervals as defined by DMID and may be made more frequently as directed by DMID. Monitoring visits will include, but are not limited to, review of regulatory files, sample tracking log, CRFs, informed consent forms, medical and laboratory reports, and protocol compliance. Study monitors will meet with investigators to discuss any problems and actions to be taken and document visit findings and discussions. The University of Rochester's IRB and other regulatory agencies may conduct study monitoring visits.

12 STATISTICAL CONSIDERATIONS

12.1 Study Hypothesis

The primary hypothesis being tested in this study is that there will be differences in the serum antibody response, specificity, quantity and quality of memory B cell derived polyclonal antibodies (MpAb) and specificity and magnitude of the HA-specific CD4 T cell response between recipients of egg-derived and recombinant vaccines.

12.2 Sample Size Considerations

The power analysis is based on the primary aim of comparison of serum antibody, specificity, memory B cell derived polyclonal antibodies (MpAb) and HA-specific CD4 T cell counts (in log scale to stabilize variance) between the group of subjects vaccinated with egg derived TIV IM and the group of subjects vaccinated with Baculovirus derived TIV IM. In this explorative study, the HA-specific CD4 T cell response to the Baculovirus derived vaccine is unknown and thus no information is available about the group difference. But our past experience indicated the coefficient of variation (CV) of HA-specific CD4 T cell counts varied between 0.25 and 0.4 [18]. If we assume CV and use percent-change differences in HA-specific CD4 T cell counts relative to the group with egg derived vaccine, with 45 subjects per group, we will have 80% power to detect at least 10% ~ 20% difference in HA-specific CD4 T cell counts between the two groups. This power analysis is based on two-sample t test with a two-sided significance level of 0.05 and equal allocation of subjects to any two groups.

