4.2 Outcome Measures

4.2.1 Primary Outcome Measures

The primary outcome measure for this study is:

- Mean change in the specificity, quantity and quality of serum antibody titers to the vaccine viruses, pH1N1, H3 and influenza B using HAI (year 1-5) and MN for pH1N1 and H3 viruses (years 1-5 from Day 0 to Day 28)

- Mean change in the CD4 T cell reactivity to pools of total pHA peptides derived from the pH1N1 HA, as well as H3, influenza B HA, NP, and M1 peptides will be quantified using cytokine Elispot From Day 0 to Day 14

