12.4 Final Analysis Plan

We will define the groups as: G1 (egg derived vaccine) = G1a (seronegative to pH1N1 virus and receiving egg derived vaccine) + G1b (seropositive and receiving egg derived vaccine); G2 (baculovirus derived vaccine) = G2a (seronegative to to pH1N1 virus and receiving baculovirus derived vaccine) + G2b (seropositive and receiving baculovirus derived vaccine). The log transformation will be applied to stabilize variance, as suggested by our past experience [18]. The between-group and among-group comparison in each of the outcomes will be based on both standard statistical analysis approaches using summary statistics and the complicated random variance model approach. Specifically, each of CD4 specific cells for different Influenza proteins (eg HA, NP etc), memory B cell derived polyclonal antibodies, HAI and MN titers among the four groups and between G1 and G2, between G1a and G2a, and between G1b and G2b, we will use maximum responses or maximum boost responses (maximum value after day 0 – value at day 0) or maximum fold increase as endpoint and do group comparison by ANOVA for among-group comparison and two-sample t-test for between-group comparison, or their nonparametric analogy of Kruskal-Wallis test and Wilcoxon Rank sum test, respectively, may also be applied for robustness. Multiple comparisons may subject to Bonferroni correction, if appropriate. Correlation test such as Pearson correlation analysis, or its nonparametric analogy of Spearman correlation analysis, will be used to study how baseline CD4 responses and/or memory B cell derived polyclonal antibodies, HAI, MN titers affect the boost responses of CD4, memory B cell derived polyclonal antibodies, HAI and MN titers after vaccination.

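### Section 12.2 gives 80% power for a difference in CD4 counts, but the primary CD4 outcome is the change from Day 0 to Day 14, so the power of the primary comparison is not shown

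*Combined protocol and SAP*

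**What the plan says.** Section 12.2 (Sample Size Considerations) works with "HA-specific CD4 T cell counts (in log scale to stabilize variance") and proposes to "use percent-change differences in HA-specific CD4 T cell counts relative to the group with egg derived vaccine". The comparison is therefore between groups, with the egg group as reference; it is not a change from baseline. The noise is the "coefficient of variation (CV) of HA-specific CD4 T cell counts varied between 0.25 and 0.4". No time point is attached to that CV. The result is that "with 45 subjects per group, we will have 80% power to detect at least 10% ~ 20% difference in HA-specific CD4 T cell counts", based on a "two-sample t test with a two-sided significance level of 0.05" and "equal allocation of subjects to any two groups".

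Section 4.2.1 (Primary Outcome Measures) defines the CD4 outcome differently: "Mean change in the CD4 T cell reactivity to pools of total pHA peptides derived from the pH1N1 HA" and other peptide pools, by ELISpot, from Day 0 to Day 14.

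Section 12.4 (Final Analysis Plan) leaves the endpoint open: the maximum response, the maximum boost over Day 0, or "maximum fold increase as endpoint". The last two use the Day 0 value. Its mixed models also compare groups on differences from baseline.

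**The concern.** A count at one time point and a change between two time points have different variance formulas. The variance of a change depends on how strongly a subject's two values are correlated, and the plan says nothing about that. The 80% is the only justification offered for 45 per group, and a reader will attach it to the primary CD4 outcome, although the calculation was made for another quantity. If the two days correlate weakly, the primary comparison is less sensitive than a comparison of counts. If they correlate strongly, it is more sensitive. In both cases the plan does not say what difference in the primary outcome the trial can detect.

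**Working it through.** **Inputs from 12.2.** 45 per group, two-sided 0.05, two-sample t test (88 df), CV 0.25 to 0.40, log scale, differences of 10% to 20%. I read 10% as paired with CV 0.25 and 20% with CV 0.40. **Assumed, because the documents do not give it:** rho, the within-subject correlation of log counts between Day 0 and Day 14. Results below use unrounded values.

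**Step 1: the plan's own figure, for counts.** From the noncentral t distribution, 80% power at 45 per group needs a standardised difference of 0.597. The log-scale SD is s = sqrt(ln(1 + CV²)), which is 0.246 at CV 0.25 and 0.385 at CV 0.40.

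- Detectable at CV 0.25: exp(0.597 × 0.246) − 1 = 15.8% up, or 1 − exp(−0.597 × 0.246) = 13.7% down. Raw scale: 0.597 × 0.25 = 14.9%.
- Detectable at CV 0.40: 25.9% up, 20.6% down. Raw scale: 0.597 × 0.40 = 23.9%.
- Power for 10% at CV 0.25: 44% up, 52% down (47% on the raw scale).
- Power for 20% at CV 0.40: 60% up, 78% down (65% on the raw scale).

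So the printed 80% for 10% to 20% does not reproduce for counts. The range is about 14–16% to 21–26%.

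**Step 2: the change.** If log counts have the same SD s on both days, the variance of log(Day 14) − log(Day 0) is s² + s² − 2 × rho × s², so the SD of the log change is s × sqrt(2(1 − rho)). The difference detectable with 80% power is exp(0.597 × SD) − 1 upward and 1 − exp(−0.597 × SD) downward. It is a ratio of fold increases between groups.

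| rho | CV 0.25: up / down | CV 0.40: up / down | Power for the change at the difference that has 80% power on counts |
|---|---|---|---|
| 0 | 23% / 19% | 38% / 28% | 51% |
| 0.3 | 19% / 16% | 31% / 24% | 66% |
| 0.5 | 16% / 14% | 26% / 21% | 80% |
| 0.7 | 12% / 11% | 20% / 16% | 95% |
| 0.9 | 7% / 6% | 11% / 10% | over 99% |

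**Step 3: the rho at which the printed statement would be true for the change.** The required SD is the log effect divided by 0.597, and rho = 1 − SD²/(2s²).

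- 10% up, CV 0.25: SD = 0.0953/0.597 = 0.160, rho = 0.79.
- 10% down, CV 0.25: SD = 0.1054/0.597 = 0.176, rho = 0.74.
- 20% up, CV 0.40: SD = 0.1823/0.597 = 0.305, rho = 0.69.
- 20% down, CV 0.40: SD = 0.2231/0.597 = 0.374, rho = 0.53.

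Below these values the change has less than 80% power for the printed difference; above them it has more.

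**Step 4: the equal-variance assumption.** With unequal SDs, the change and the Day 14 count have equal variance when rho = SD(Day 0)/(2 × SD(Day 14)). That is 0.5 if the SDs are equal, 1/(2 × 1.5) = 0.33 if the Day 14 SD is 1.5 times the Day 0 SD, and 1/(2 × 0.8) = 0.63 if it is 0.8 times. The break-even point therefore moves with a quantity that the plan also leaves out.

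**The case against.** Several points on the other side are sound. Under randomisation and on the log scale, the group difference in change targets the same ratio as the group difference in Day 14 counts, so only precision is in question. The first endpoint named in 12.4, the maximum response, is itself a count, so the mismatch with the analysis plan is partial. Section 12.2 calls the study exploratory and says that nothing is known about the group difference. All of this limits the consequence, but none of it supplies the SD of the outcome that 4.2.1 names as primary.

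A reader might also infer more than the documents support:

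- *That the primary comparison is underpowered, or that the variance of the change is known to differ.* Neither follows. At equal variances the change is noisier than a count below rho 0.5 and less noisy above it, and no rho is given.
- *That the CV is a between-subject one.* Section 12.2 does not label it.
- *That the printed power carries over exactly at rho 0.5.* It does not. At rho 0.5 the change has the power of counts, which for the printed pairs is 44–52% and 60–78%, not 80%. The last column of the table starts from a difference chosen to give 80% on counts, not from the printed 10% to 20%.
- *That the formula covers all of 12.4.* It describes a log change between two fixed days. The maximum boost and maximum fold increase run over post-vaccination samples on days 3, 7, 14 and 180 (section 9.2.1) and have other variances.

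**Conclusion.** The concern holds as a gap between the power calculation and the primary outcome. The 80% in 12.2 is stated for a difference in counts, the primary CD4 outcome is a change, and nothing in the plan carries the variance from one to the other. The size depends on rho: between rho 0 and 0.7 the detectable increase falls from 23% to 12% at CV 0.25 and from 38% to 20% at CV 0.40. These figures assume equal log-scale variance on the two days and that the quoted CV applies to counts at those days. The direction of the error is unknown, and a loss of power should not be asserted. Because the printed range fails for counts as well, correcting that arithmetic alone would still leave a figure for a quantity other than the primary outcome.

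**What to change.** Recompute 12.2 for the outcome in 4.2.1. If paired Day 0 and Day 14 CD4 assays from completed seasons are available, use the SD of the log Day 14/Day 0 ratio. Such data are plausible, since 9.2.1 schedules CD4 assays on both days and 12.3.2 plans yearly immunogenicity analysis, but they are not documented: the results reported in 3.2 are antibody results. If they are not available, state the CV with its time point, show a range of rho, and write out the equal-variance assumption.

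State the ratio of fold increases between Flublok and Fluzone SD that is detectable with 80% power at 45 per group. Delete the count-based sentence, or keep it with corrected arithmetic and label it as applying to a count at a single time point.

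The cost is one calculation and a reworded paragraph, with no change to design or conduct. The drawback is that the stated figure may become less favourable.
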